The primary outcomes are motor control, as measured by the upper extremity Fugl-Meyer; ADL function; and grip strength as measured by a dynamometer; a custom metric to determine Kinematic workspace and dynamic workspace will be employed. Customized metrics will be defined such as movement time, movement velocity, and accuracy. New outcome variables related to MRI: fiber density and hemisphere activation

Secondary outcome variable(s)

The secondary variables for motor impairment are upper extremity coordination, finger dexterity, and spasticity - the Box and Block and Ashworth assessments will be used to evaluate these.

Background

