Part A Usability Study: Cross-sectional study comparing outcome variables for stroke survivors with varying levels of motor deficit impairment in their upper extremity. Subjects with mild motor deficits will be compared against stroke survivors with severe motor deficits after completing exercises with both commercial and custom therapy devices. Therapy exercises will be performed in random order, decided prior to the session. It will be randomly determined which robot the patient will use first, the order of operating modes used for the new robot, and the order of therapy exercises performed in each mode. Surface Electromyography (EMG) will be used in order to detect the small electric currents, or signals, which are generated by muscle activity. The collection of the strength and pattern of the signals will permit us to verify muscle activity over time. Part B Therapy Study: Pre-post study looking at change in outcome variables over 12 therapy sessions (three times a week for one month). Only low and mid functioning stroke survivors will be asked to participate in Part B of the study, and only the custom haptic device will be used by the study subjects. Pre-post evaluations will be administered at session 1 and 12. Surface Electromyography (EMG) will be used in order to detect the small electric currents, or

signals, which are generated by muscle activity. The collection of the strength and pattern of the signals will permit us to verify muscle activity over time.

Study duration

1) We estimate that it will take 3 years from the date of IRB approval to enroll all subjects and complete the study. 2) Part A - The subject's participation in the study will be limited to approximately 4 hours; 1-2 hours to be evaluated by a therapist with expertise in stroke rehabilitation and 2-3 hours of assessing the viability and usability of the various therapy devices. Part B - Subjects enrolled in Part B will be asked to return 3 times a week for 1 month (12 sessions). All sessions will last approximately 1.5 hours. 3) Projected date of the proposed study: 3/1/14 to 7/1/17.

Resources necessary for human research protection

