Part A: Participation in this part of the study will include the following steps: 1) Informed Consent: After arrival, subjects will review and sign the consent form with study personnel present. 2a) Pre-Assessments: A member of the research team will evaluate the subjects' affected arm and assess their ability to use it. Subjects will be evaluated using a battery of assessments in order to determine their level of impairment such as the Beck Depression Inventory, Upper Extremity Fugl-Meyer, Montreal Cognitive Assessment, Jebson Taylor, Box in Block, Modified Ashworth, and grip strength using a dynamometer, etc. 2b) Workspace Assessment: The protocol for the kinematic workspace would entail of moving patients upper extremity in a series of motions that mark the key points of their workspace. This would include movement with extended elbow to manipulate the shoulder joint in the cardinal directions (e.g. horizontal movements at the abdominal and shoulder levels, and vertical movements at 0, 45, 90 and 135 degrees), internal/external rotation of the shoulder, as well as functional movements of the arm. For the functional movements the patient would be asked to touch six points on their body, the left and right sides of their hips, their left and right shoulders, their mouth and the top of their head while being monitored by a Kinect camera. These actions are chosen as they cover areas necessary for ADLs such as eating, grooming and toileting and covers motion in clinically relevant planes. Each participant would be also given the standard clinical score. The movement protocols would be repeated under a loading condition where light weights (0.5-1lb) would be attached to subjects wrist. Given the additional mass, we would determine the change in the kinematic workspace space as well as the change in the joint torques. The protocol for recovery of dynamics would entail of the a series of motions using the TheraDrive systems as described in Theriault, A., Nagurka, M., Johnson, M.J: Therapeutic Potential of Haptic TheraDrive: An Affordable Robot/Computer System for Motivating Stroke rehabilitation, in: 5th IEEE RAS&EMBS International Conference, pp.415-420, 2014. The TheraDrive would be positioned at various locations in the subjects workspace (e.g. closer to the torso, away from the torso, higher/lower). The ability to exert specific torques at these locations would provide information on the dynamic capacity of the muscles within various points of the workspace. 3) Break:

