
Subjects will be given a 15 minute break. 4) First Therapy Device: Subjects will be introduced to several robots: a wheel, joystick, and custom crank chosen randomly (like the flip of a coin). First, they will be trained in the use of all robots and their safety features. Following training, they will be asked to move each robot into different positions, first without pressure applied to the handle, and then with pressure applied to the handle. After each exercise they will be asked about their level of exercise and level of pain discomfort. After subjects finish all exercises with a robot, they will be given a survey about the robot. They will also be given surveys to discuss their experience with the device and their level of motivation for use of them. The surface EMG may be utilized during the entirety of the participant's interaction with the novel therapy device. Prior to its placement on the subject, the reason for its use will be thoroughly explained. 5) Break: Subjects will be given a 15 minute break. 6) Subsequent Therapy Device: Subjects will be instructed in the use of another robot. The same procedure will be followed as in the first evaluation. The surface EMG may be utilized during the entirety of the participant's interaction with the novel therapy device. Prior to its placement on the subject, the reason for its use will be thoroughly explained. 7) Final Survey: Subjects will be given a survey asking them to evaluate the robots and indicate which robot they prefer. Part B: For subjects invited to participate in Part B of the study - only low functioning stroke survivors are eligible - participation in this part of the study will include the following steps: 1) Informed Consent: After arrival, subjects will review and sign the consent form with study personnel present. 2a) Pre-Assessments: If subjects are only participating in Part B of the study, at their first visit, a member of the research team will evaluate their affected arm and assess their ability to use it. Subjects will be evaluated using a battery of assessments in order to determine their level of impairment such as the Beck Depression Inventory, Upper Extremity Fugl-Meyer, Montreal Cognitive Assessment, Jebson Taylor, Box in Block, Modified Ashworth, and grip strength using a dynamometer, etc. If a study subject participated in Part A, they will not be reevaluated by a therapist. 2b) Workspace Assessment: Same as in Part A 2) Custom Therapy Device: Subjects will be introduced to the custom robot. They will be trained in the use of this robot and its safety features (1st session). Following training, they will be asked to move the robot into different positions. After each exercise subjects will be asked about their level of exercise and level of pain discomfort. Subjects will continue to work with the custom therapy device for 12 sessions over the course of one month. The surface EMG may be utilized during the entirety of the participant's interaction with the novel therapy device. Prior to its placement on the subject, the reason for its use will be thoroughly explained. 3) Motivation Questionnaire: At the end of their 1st and 12th sessions, subjects will be asked to complete a questionnaire assessing their level of motivation. 4) Post-Study Survey: After their last session, subjects will be asked to complete a survey assessing the robot. 5) Post-Study Assessment: After their last session, a certified therapist will evaluate the participants' affected arm and assess their ability to use it. In addition, they will also be evaluated for depression and a mental health assessment will be given.

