Subjects may experience fatigue or muscle strain if exercises are too intense. In the event of a robot malfunction, subjects may experience muscle strain or minor bruises. To minimize risk of injuries due to exercise, the intensity will be kept in the mild to moderate range. Exercise intensity must also be kept low in order to reduce the confounding effect of fatigue on experimental results. After each exercise, subjects will be questioned regarding the difficulty of the task, exercise intensity, and their discomfort level. At that time, the protocol will be adjusted accordingly. Subjects will be given ample time to rest as part of the experiment protocol. Risk of injury from the robot stems from its ability to exert large forces. Therefore, we have implemented several layers of protection to prevent the robot from exerting forces that might cause injury. For example, the software permits the robot's commanded force to be limited and a stop command to be issued to the robot. In addition, the current to the motor that determines the forces is limited by a current limiter that will maintain current to a preset level. As a backup, there is a limit switch that will cut power to the motor if excessive forces are detected. And as a final level of backup, another mechanical method (torque limiter) has been put in place that limits forces and is capable of physically disengaging the motor from the handle that the patient is gripping. A spring inside the robot allows it to be compliant, which reduces the ability of patients to feel sudden starts or stops of the motor, and reduces the risk of injury in the event of a robot-patient collision. Padding on the robot provides further protection against any impacts. Furthermore, an emergency stop switch will be made available to both the subject and operator; it will cut power to the motor when triggered. If a subject is experiencing a level of pain great than three (mild) on the Visual Analog Pain Scale, the session will be stopped.

Potential Study Benefits

There are no direct, major benefits to a particular subject. Participation will help advance rehabilitation robotics research.

Alternatives to Participation (optional)

Data and Safety Monitoring

The principal investigator will monitor this protocol. See attached for the D&SM Plan.

The following documents are currently attached to this item:

There are no documents attached for this item.

Risk / Benefit Assessment

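### The wrist-weighted workspace movements come second, so the effect attributed to the added mass cannot be separated from fatigue or practice

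*Combined protocol and SAP*

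**What the plan says.** The Procedures section (Part A, step 2b, Workspace Assessment) lists a series of arm movements: horizontal movements at two levels, vertical movements at four angles, shoulder rotation, and touching six points on the body under a Kinect camera. It then states: "The movement protocols would be repeated under a loading condition where light weights (0.5-1lb) would be attached to subjects wrist". The intended contrast follows: "Given the additional mass, we would determine the change in the kinematic workspace space as well as the change in the joint torques". Part B uses the same workspace procedure.

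Under Primary outcome variable(s), the plan says that "a custom metric to determine Kinematic workspace and dynamic workspace will be employed".

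Order is controlled elsewhere. The Design section says "Therapy exercises will be performed in random order, decided prior to the session", and the list of what is randomised covers the first robot, the operating modes of the new robot and the exercises within each mode. Load condition is not on it.

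The first scheduled rest in Part A comes after the whole workspace assessment and just before the robots: "Subjects will be given a 15 minute break. 4) First Therapy Device". Potential Study Risks adds general provisions: "Exercise intensity must also be kept low in order to reduce the confounding effect of fatigue on experimental results", together with an undertaking to allow enough rest and to adjust the protocol after questioning subjects about each exercise.

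The Analysis Plan says that Kinect data will be assessed and fitted to a limb model. It names no test for loaded against unloaded and includes no order term.

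**The concern.** A repeat comes second. If loaded movements always follow unloaded ones, anything that changes between the first and second pass is credited to the weights. A smaller loaded workspace could be fatigue. A loaded workspace that holds up well could be practice offsetting a real load effect. The plan itself recognises fatigue as a confounder.

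What is at stake is whether the load effect on workspace and joint torque can be interpreted. The problem is structural: once the data are collected in this order, no model can recover the load effect. It therefore has to be settled in the procedure.

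**Working it through.** The plan gives no power, effect size or SD for this contrast, so there is no figure to reproduce.

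**1. Can load be separated from order?** For one subject write y = a + βL + πP, with L = 1 if loaded, P = 1 for the second pass, β the load effect and π the order effect (fatigue plus practice).

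- Fixed order: unloaded gives a and loaded gives a + β + π. The difference is β + π. The design matrix (intercept, load, period) has rank 2 for 3 parameters, so only the sum can be estimated. Adding a period term to the analysis would not help.
- Both orders used: second minus first is π + β in one sequence and π − β in the other. Half the difference between the sequences is β. The rank is 3, and the effects separate if there is no differential carry-over.

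If each movement were instead repeated with weight straight after its unloaded version, load would still be second and the fixed-order result would still apply.

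**2. How large might it be?** This is hypothetical. Suppose a two-sided paired t-test at 0.05 were applied, the true load effect were zero, and the order effect were d SDs of the paired difference. The non-centrality is d√n. The values of n are the two totals in the documents (about 36 in the Abstract, 56 under Accrual); the values of d are assumptions.

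| d | n = 36 | n = 56 |
|---|---|---|
| 0.1 | 0.09 | 0.11 |
| 0.2 | 0.22 | 0.31 |
| 0.3 | 0.42 | 0.60 |
| 0.5 | 0.83 | 0.96 |

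These are probabilities of declaring a load effect that does not exist. With load order counterbalanced, the simulated rate was 0.049 to 0.052 for d of 0.2 and 0.5 at both sample sizes (40,000 replicates each).

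**3. Does an unloaded repeat afterwards repair it?** That depends on where it is placed. Counting the listed movements gives 2 + 4 + (1 or 2 for rotation) + 6 = 13 or 14. Assume even spacing and linear drift.

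- Listed order, 14 movements, touch points repeated unloaded at the end: the touch points sit at positions 9–14 (mean 11.5), 23–28 loaded (25.5) and 29–34 (31.5). The simple mean of the unloaded runs is (11.5 + 31.5)/2 = 21.5. The uncorrected drift is 25.5 − 21.5 = 4 positions, against 25.5 − 11.5 = 14 without the repeat: 4/14 = 29% remains.
- With 13 movements: means 10.5, 23.5 and 29.5; the simple mean is 20; 3.5/13 = 27% remains.
- Interpolating to the time of the loaded run: the weight on the later run is 14/20 = 0.70 (14 movements) or 13/19 = 0.68 (13 movements), so about 0.3 before and 0.7 after. Linear drift cancels.
- Adjacent blocks of six (positions 1–6, 7–12, 13–18, means 3.5, 9.5 and 15.5): (3.5 + 15.5)/2 = 9.5, so linear drift cancels with a simple mean.

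**The case against.** The strongest reply is that this is one exploratory contrast in a self-described pilot, with light weights, low intensity and a general promise of rest. Much of that stands, and it limits the point in five ways.

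- **Primary outcome.** A reader might infer that a primary outcome is biased. The documents list workspace, not load-induced change in it, and the unloaded workspace is measured before any weight is attached. Comparisons made under the same fixed order, between groups or before and after therapy, are less affected.
- **Error rate.** A reader might infer an inflated type I error. The two named tests (the Part A ANOVA and the Part B paired t-test) are given for tracking accuracy. None is attached to this contrast, so no stated alpha or power is affected.
- **Severity groups.** A reader might infer a spurious low-versus-high difference in sensitivity to load. No such comparison is planned: the group comparisons concern robot-based metrics and tracking error.
- **Rest.** It would be wrong to say that the plan ignores fatigue. The general provisions may reduce it. They are not tied to the interval between the two sets, however, and rest does not remove practice.
- **Order and movement count.** The order is inferred from the wording rather than stated as a rule. The cardinal movements are given as examples, so 13 or 14 is illustrative, and only the six touch points are clearly performed by the patient.

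None of this separates load from order. Pilot status does not help either, since a load effect that cannot be interpreted cannot inform later work.

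**Conclusion.** The point holds for the loaded-minus-unloaded contrast in kinematic workspace and joint torque. On the natural reading of step 2b, load is completely aliased with order, so the plan as written yields β + π and attributes it to mass. This conclusion needs no assumption beyond the loaded set coming second.

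The size and sign of π are unknown: fatigue and practice pull in opposite directions, and the documents give no drift or SD. The false-positive figures above only illustrate what a modest order effect could do under a test that the plan does not specify. The harm is to interpretation of this one contrast.

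**What to change.** Keep the unloaded set first, but run the six touch points as adjacent unloaded, loaded and unloaded blocks. For these points, define the load effect as the loaded value minus the mean of the two unloaded blocks. This removes linear drift; drift that levels off or accelerates is only partly removed.

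If the listed order is kept and the touch points are repeated unloaded at the end, interpolate the two unloaded runs to the time of the loaded run (weights of about 0.3 before and 0.7 after, or from recorded times) instead of taking a simple mean.

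Report the load effect on movements that are not bracketed as confounded with order.

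The alternative is to randomise loaded or unloaded first within function group and include a period term, assuming no differential carry-over. Whichever is chosen, state the order explicitly in step 2b and the contrast in the Analysis Plan.

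Cost: bracketing adds six unloaded touch movements, a few extra minutes of arm movement per assessment. Randomising adds no movements, but the unloaded workspace is then measured second in half the subjects.

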TheraDrive is a low-cost robotic system for post-stroke upper extremity rehabilitation. The system uses off-the-shelf computer gaming wheels with force feedback to help reduce motor impairment and improve function in the arms of stroke survivors. Preliminary results from various studies have shown that the original TheraDrive system lacked a robust mechanical linkage which could withstand the forces exerted by patients, lacked a patient-specific adaptive controller to deliver personalized therapy, and was not capable of delivering effective therapy to severely low-functioning patients. A new low-cost, high-force haptic robot with a single degree of freedom has been developed to address these concerns. This study has two purposes: first, to test the viability and usability of the new robot system alongside the original TheraDrive system; and second, to test if low-functioning patients benefit, and if so how much, from using force-feedback therapy as opposed to devices with zero impedance. This will be done by recruiting approximately 36 human subjects. Exercises will be performed by study subjects and an adaptive controller will monitor patient performance to ensure that exercises are difficult but doable, which is important for maintaining patient motivation. We hypothesize that not only will the new system be viable, but that it will provide better robot-assisted therapy to a large variety of patients, especially low-functioning stroke survivors with hemiplegia.

Objectives

Overall objectives

This study is being performed to assess the usability of affordable force-feedback devices for stroke rehabilitation. For this pilot study, subjects will use two or more devices (a commercial force-feedback

joystick, commercial force-feedback wheel, and a custom force-feedback device) to complete games and exercise tasks to determine the ease of using these devices and their impact on motor performance and function. The long-term goal of this project is to develop an inexpensive high-force haptic rehabilitation robot that can safely be used by patients at home without therapist supervision. A sub-goal was to simulate the human-machine interaction. We will use our assessment tools to determine upper arm kinematic and dynamic workspace recovery

Primary outcome variable(s)

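### Part A randomises only the first robot by a coin-like method; later device order is unspecified, not balanced within function group and absent from the ANOVA

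*Combined protocol and SAP*

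**What the plan says.** Part A compares devices within the same person. Under Overall objectives, "subjects will use two or more devices". In the Procedures for Part A (steps 3 to 7) the devices follow one another with a short rest between them: "Subjects will be given a 15 minute break".

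On order, the Design section says "It will be randomly determined which robot the patient will use first". It adds random order for the new robot's operating modes and for the exercises; of the exercises it says "Therapy exercises will be performed in random order, decided prior to the session". Step 4 of the Procedures describes the robots as "a wheel, joystick, and custom crank chosen randomly (like the flip of a coin". Step 6, on what follows the first device, says only "Subjects will be instructed in the use of another robot". No section gives a sequence list, blocking, counterbalancing or stratification by function group.

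Item 2 of the Analysis Plan compares tracking error across low and high function groups and across devices, using a two-way ANOVA at alpha 0.05. It names no position, sequence or repeated-measures term. Potential Study Risks recognises that position could matter: "Exercise intensity must also be kept low in order to reduce the confounding effect of fatigue on experimental results".

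The Abstract gives "approximately 36 human subjects", while Accrual gives 56 for Parts A and B together. The number for Part A alone is not stated.

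**The concern.** When one person uses several devices in succession, a score reflects the device and also its place in the sequence. Subjects may improve because the same procedure is repeated, or worsen because they tire. Unless each device falls equally often in each position, part of the position effect enters the device contrast. Unless the balance is the same in both function groups, part of it also enters the device-by-function contrast. That second contrast carries the Abstract's hypothesis that the new system helps low-functioning survivors in particular.

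The plan neither prevents this by design nor adjusts for it in the analysis. Its wording also leaves open two situations with different consequences: a fully random order, where the cost is precision, and a random first device followed by a habitual order, where the cost is bias.

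**Working it through.** The plan gives no figure for order balance, so there is none to reproduce. The checks below rest on stated assumptions.

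**Inputs.** Three devices (Procedures, step 4). Two function groups (Analysis Plan, item 2). Group size *n* is assumed: 18 is half of the Abstract's 36; 28 is half of the 56 in Accrual, an upper end because that total includes Part B; 10 is a low case. Each later position is assumed to shift the score by *d*, equally for every device. The documents give no value for *d*, so results are per unit of *d*.

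**1. First device only.** If each device is first with probability 1/3, the number in a group who start with the custom robot is Binomial(*n*, 1/3). At *n* = 18 the mean is 18/3 = 6 and the SD is √(18 × 1/3 × 2/3) = 2, with a 95% range of 2 to 10. The probability that the two groups differ by at least 20 percentage points in custom-first share is 48% at 10 per group, 22% at 18 (a gap of 4 or more subjects) and 12% at 28.

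**2. Whole order simply randomised.** Over the six orders of three devices, the position difference between two given devices is +1 or −1 in two orders each and +2 or −2 in one order each. Its mean is 0 and its variance is (4 × 1 + 2 × 4)/6 = 2. The error that position adds to the device-by-function contrast therefore has mean 0 and SD *d* × √(2/*n* + 2/*n*):

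- *n* = 10: √(4/10) = 0.63*d*
- *n* = 18: √(4/18) = 0.47*d*
- *n* = 28: √(4/28) = 0.38*d*

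To judge whether this matters, let *s* be the within-subject residual SD. The residual part of a two-device difference has variance 2*s*² and the position part has variance 2*d*². The standard error is therefore inflated by √(1 + *d*²/*s*²): 3% at *d* = 0.25*s*, 12% at 0.5*s* and 41% at *d* = *s*.

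**3. First device random, the rest in a fixed order.** Suppose the remaining devices always follow the order wheel, joystick, crank. The three possible sequences are wheel–joystick–crank, joystick–wheel–crank and crank–wheel–joystick. Mean positions are:

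- wheel: (1 + 2 + 2)/3 = 1.67
- joystick: (2 + 1 + 3)/3 = 2.00
- crank: (3 + 3 + 1)/3 = 2.33

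Any other fixed order gives the same three values to different devices. The extreme pair differs by 2.33 − 1.67 = 0.67 positions, so their contrast is biased by 0.67*d* at every sample size. In the device-by-function contrast this bias cancels if *d* is the same in both groups. If the groups tire or learn at different rates, 0.67 × (*d* low − *d* high) remains.

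**4. Only two devices, the same two for everyone.** The first choice then fixes the whole order, so the situation in step 3 cannot arise. The position difference is ±1, with variance 1, and the SD in step 2 becomes *d* × √(2/*n*): 0.45*d*, 0.33*d* and 0.27*d*.

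**5. Balanced lists.** With 18 per group and permuted blocks of six, each order occurs 18/6 = 3 times and each device is first 6 times in each group, so the error in step 2 is zero. With an incomplete last block, first-device counts within a group differ by at most 2. Under simple randomisation at *n* = 18 the median gap between the most and least frequent first device is 4, and the 95th percentile is 8.

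**The case against.** The best defence is that randomisation is present and the study is a pilot of usability. If the whole order is random, additive position effects go into within-subject error, a suitable within-subject test stays valid, and only precision is lost; step 2 shows that the loss is small unless position effects approach the residual SD. The plan also limits those effects: training on all robots comes before testing, there is a break between devices, and intensity is kept low because of fatigue. If every subject uses the same devices, a position effect common to everyone cancels in the low-versus-high main effect, which is the difference that the Analysis Plan says the ANOVA will detect.

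All of this stands, and it limits the weight of the point. It does not remove it. The mitigations may shrink position effects but do not balance them, and the defence assumes a fully random order that the plan does not specify.

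A reader might infer more than the documents support:

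- That order will be unbalanced. Exact balance is unlikely, but material imbalance is a chance event.
- That the comparison is biased. This follows only if later devices take a fixed order, on which the text is silent.
- That some subjects will use two devices and others three. The objectives permit this but do not say it is planned.
- That a device-order list is already required. The advance decision in the Design section concerns exercises.
- That a literal coin is meant for three devices. The phrase may be a lay description.
- That Part A is a declared crossover. The Design section calls it cross-sectional, although device use is within-subject.

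**Conclusion.** The point holds as one of incomplete specification and a missed, inexpensive control. Only the first robot is stated to be random, later order is undefined, order is not balanced within function group, and the planned ANOVA does not account for position. Under a fully random order the consequence is chance error in the device and device-by-function contrasts, not bias. For the latter its SD is 0.38 to 0.63 units per one-unit position shift across the assumed 28 to 10 per group. Under a fixed later order with three devices, the extreme pair is systematically 0.67 positions apart.

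These sizes rest on assumed group sizes, on three devices per subject, and on an equal shift per position whose magnitude the documents do not give. Priority is low: a worthwhile improvement to a pilot, with no ground for calling the group comparison invalid.

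**What to change.** State how the complete device order is generated. Use the six orders of three devices in permuted blocks of six, or the two orders in balanced blocks if only two devices are used, with separate lists for the low and high function groups. Draw the order once the pre-assessment has classified the subject, and state the cut-off for that classification. State which devices every subject uses. Replace the plain two-way ANOVA with a within-subject (repeated-measures) model containing function group, device, their interaction and position.

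This needs no extra subjects or data. The costs are two order lists to keep, a function class that must be known before the order is drawn, and an additional model term. Balance is only approximate with incomplete blocks or dropout; the position term covers what remains.
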